4.2. RATIONALE FOR CURRENT STUDY

Inhaled corticosteroids are effective treatment at all ages for patients with eosinophil airway disease, but have side-effects, including growth suppression, adrenal failure and increased susceptibility to respiratory infection. Only some children with preschool wheeze have airway eosinophilia, and thus benefit from inhaled corticosteroids, but these cannot be distinguished from the non-eosinophil phenotypes clinically. By using three simple point of care tests (blood eosinophil count, skin prick test to aeroallergens and FeNO) we aim to select out the subgroup of responders who will benefit, while avoiding exposing non-responders to potential side-effects.

4.3. PRE-CLINICAL/CLINICAL DATA

This highly variable pathophysiology of pre-school wheeze is reflected in the response to treatment, making the determination of phenotype much more than a matter of academic importance. In the first serious attempt to apply personalised medicine to this group of patients, the INFANT study investigators used a three way crossover design to compare the differential response to therapy with intermittent ICS, regular ICS and montelukast in 300 children (15). Sixty improved spontaneously over the duration of the study. Atopic sensitisation predicted a good response to ICS, shown by reduced numbers of attacks of wheeze and better control of chronic symptoms. In a retrospective analysis, an elevated blood eosinophil count and even better, a combination of positive SPTs and peripheral blood eosinophils $>300/\mu\text{l}$ were the best predictors of a good response to regular ICS. Leukotriene receptor antagonists were not beneficial in any group. Those with no positive SPTs or elevated eosinophil count rarely had acute attacks of wheeze. These findings, especially the predictive power of blood eosinophil count, need to be tested prospectively in primary care, the setting in which most of these children are treated, in a large prospective randomised controlled trial. Prior to this, pilot data to inform power calculations, and the feasibility and

acceptability of this approach needs to be determined. Additionally, although FeNO in preschool children is not well standardized there is one study which proposed FeNO values ≥ 10 ppb to be predictive of eosinophil inflammation in preschool children (16).

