5. STUDY'S AIM AND OBJECTIVES

AIM: To obtain pilot data to test the hypothesis that aeroallergen sensitisation (confirmed by a wheal formation with a diameter ≥ 3 mm after a skin prick test is performed), FeNO (offline method) ≥ 10 ppb and a peripheral blood eosinophil count $\geq 300/\mu\text{l}$, alone or in combination, can predict future wheezing exacerbations in preschool children as well as response to treatment with inhaled corticosteroids, as a preliminary to a large, randomised controlled trial. Also, that these tests are acceptable to families.

OBJECTIVES:

- To recruit 100 preschool children with a history of wheeze, aged one to five years old, and determine atopic status, peripheral blood eosinophil count (point of care test) and FeNO (offline method).
- To evaluate the feasibility and acceptability of these tests
- To categorize the children according to the biomarkers tested and assess whether any or all, alone or in combination, predict future wheezing exacerbations as well as determine the clinical outcome over one year
- To obtain parents' and doctors' insights into whether the biomarkers mentioned above could be used in a future intervention study.

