6.1. STUDY OUTCOME MEASURES

Primary outcome:

Acute attacks of wheeze defined as requiring an unscheduled health care visit

Secondary outcomes:

- Carer days off work
- Days the child unable to attend childcare facility
- Use of oral corticosteroids
- Use of inhaled β -2 agonist (rescue therapy)
- Assessment if children's respiratory or wheezing condition is under control by using the TRACK™ score questionnaire (Test for Respiratory and Asthma Control in Kids) (Appendix 3).

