11. STATISTICS AND DATA ANALYSIS

The statistical analysis of the project will be done by [name] in collaboration with [name] (University of Edinburgh) and the Asthma UK Centre for Applied Research (AUKCAR), the funder of the study. Statistical analyses will use the GraphPad PRISM software package. A normality test will be performed to assess normal (Gaussian) distribution (e.g., the Shapiro-Wilk test. If there is normal distribution, then parametric tests will be used, otherwise non-parametric tests. Level of significance is set as a p value <0.05. The tests that are currently planned to be used are:

- **Chi-Squared test (x²-test)**

This test allows assessing if a variable is similar between two or more groups or to test if two or more variables are related/dependent

- **Fisher's Exact test**

This test is used when chi-squared values are <5, usually with a small sample size.

- **Student t-test or Mann-Whitney test**

These tests are used for comparison between two study groups. The first is for normally distributed quantitative variables and the second for non-normally distributed quantitative variables.

Data and all appropriate documentation will be stored for a minimum of 10 years after the completion of the study, including the follow-up period.

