19.4. APPENDIX 4: MONTHLY QUESTIONNAIRE

Introduction: Please take a moment to complete the following questionnaire relating to your child's wheezing condition. The questions will help us identify wheezing exacerbations and assess your child's quality of life.

Question 1: Did your child experience any wheezing symptoms during the last month?

Not at all	Once or twice	Once every week	2 or 3 times a week	4 or more times a week
				

Question 2: Was the child unable to go to childcare because of breathing problems?

Yes	No	N/A
		

If **yes**, please state how many days: _____ (Number)

Question 3: Did you have to take your child for an emergency appointment with your GP, urgent care or hospital because of wheezing?

Not at all	Once or twice	Once every week	2 or 3 times a week	4 or more times a week
				

Question 4: Was your child treated with inhaled or oral corticosteroids?

Yes	No
	

If **yes**, what was the dose, frequency and duration?

Dose:	Frequency:	Duration:
_____	_____	_____

Question 5: Was your child given β 2 agonists (blue inhaler, rescue therapy)?

Yes	No
	

If **yes**, what was the dose, frequency and duration?

Dose:	Frequency:	Duration:
_____	_____	_____

Question 6: Did you have to take days off work because your child had wheezing or breathing difficulties?

Yes	No
	

If **yes**, how many days did you take? Specify number: _____ (days)

Survey's ending message: "We thank you for your time spent taking this survey. Your response has been recorded."

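### Section 11 plans only tests read at p<0.05 and pre-specifies none of the estimates a later trial's power calculation needs; with 100 children a moderate marker effect can be missed

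*Combined protocol and SAP*

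**What the plan says.** Section 4.3 argues that the markers should be tested in a large randomised trial and sets out what must come first: "Prior to this, pilot data to inform power calculations", alongside evidence on feasibility and acceptability. Section 5 sets the size, "To recruit 100 preschool children with a history of wheeze, aged one to five years old", and the third objective is "To categorize the children according to the biomarkers tested and assess whether any or all, alone or in combination, predict future wheezing exacerbations". The primary outcome in Section 6.1 is "Acute attacks of wheeze defined as requiring an unscheduled health care visit". Section 6.1 does not say whether this is analysed as a count, a rate, or any attack against none.

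Section 11 is the whole statistical plan. After a normality check it introduces its list with "The tests that are currently planned to be used are" and names chi-squared, Fisher's exact, and Student's t or Mann-Whitney. It adds "Level of significance is set as a p value <0.05". No test is assigned to any outcome, and no estimate or interval is mentioned. No section derives the target of 100 from power or precision.

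Appendix 4, Question 3, is the monthly item that captures the primary outcome: "Did you have to take your child for an emergency appointment with your GP, urgent care or hospital because of wheezing". The answer is a tick in one of five frequency bands, from none up to four or more times a week. No number of visits is requested.

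**The concern.** A sample-size calculation takes an event rate or proportion, its spread between children, and the share of children who are marker-positive. A p-value from any test in Section 11 supplies none of these. If the plan is followed as written, nothing commits the investigators to producing those inputs. The choice between count, rate and any-attack would be made after the data are seen.

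The second risk lies in how the result is read. With 100 children split into unequal marker groups, p≥0.05 is a likely outcome even when a marker has a moderate real effect. Without a confidence interval, the reader cannot tell a marker with no effect from one the study was too small to resolve.

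**Working it through.** **Inputs.** From the documents: 100 children (Section 5), one year of follow-up each (Section 6), significance at 0.05 (Section 11; sidedness is not stated, so two-sided is assumed). There is no power or precision figure to reproduce. Assumed, because the documents give no values: marker-positive share 20% to 40%, mean μ of 0.8 to 2.5 attacks per child-year, negative binomial dispersion k of 0.5 to 1.5 (variance μ + kμ²).

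**Power for a rate ratio (RR).** With n₁ marker-positive and n₀ marker-negative children, and one common μ used for both groups as a simplification:

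SE(log RR) = √[(1/n₁ + 1/n₀)(1/μ + k)], power ≈ Φ(ln RR / SE − 1.96), RR detectable with 80% power = exp(2.80 × SE).

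- *Least favourable corner* (n₁ = 20, n₀ = 80, μ = 0.8, k = 1.5): SE = √(0.0625 × 2.75) = 0.415. RR 1.5: 0.405/0.415 − 1.96 = −0.98, power 16%. RR 2: 0.693/0.415 − 1.96 = −0.29, power 39%. Detectable RR = 3.19.
- *Most favourable corner* (n₁ = 40, n₀ = 60, μ = 2.5, k = 0.5): SE = √(0.04167 × 0.9) = 0.194. RR 1.5: 2.09 − 1.96 = 0.13, power 55%. RR 2: 3.58 − 1.96 = 1.62, power 95%. Detectable RR = 1.72.

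**Check with the kinds of test Section 11 lists.** These use marker prevalence 20% to 50%.

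| Comparison | Power at N = 100 |
|---|---|
| Mann-Whitney on simulated counts (mean 0.8 to 2.0, k 0.5 to 1), RR 1.5 | 20% to 48% |
| Same, RR 2 | 41% to 91% |
| Any attack, 30% against 45% (two proportions) | 26% to 34% |
| Any attack, 30% against 60% | 70% to 87% |
| Any attack, 10% against 40% | 85% to 95% |

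Fisher's exact test with groups of 30 and 70 gives 27% for 30% against 45%, and 79% for 30% against 60%. The methods agree: power is about half or less for a moderate effect, and often adequate for a large one.

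**What 100 children can estimate.**

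- Proportions (Wilson 95% CI): an observed 20% gives 13% to 29%; 30% gives 22% to 40%; 40% gives 31% to 50%.
- Overall attack rate, μ = 1.5, k = 1: SE of the log rate = √[(1/1.5 + 1)/100] = 0.129, so 1.5 × exp(±1.96 × 0.129) = 1.16 to 1.93.
- Risk ratio, 45% of 30 against 30% of 70: SE = √[0.55/13.5 + 0.70/21] = 0.272, so 1.5 × exp(±1.96 × 0.272) = 0.88 to 2.56. This is not significant, yet compatible with more than a doubling of risk.

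**How an estimate would feed the later trial.** Take, for illustration, a 30% relative reduction and 90% power. A control proportion of 40% (against 28%) needs [1.96√(2 × 0.34 × 0.66) + 1.28√(0.40 × 0.60 + 0.28 × 0.72)]² / 0.12² ≈ 326 per arm. Across the 31% to 50% interval the requirement runs from 471 down to 228 per arm. That range is what a pilot should deliver, and it comes from a proportion with its interval.

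**The case against.** Four points can be made for the plan.

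*Power inputs are not the only purpose.* Section 4.3 puts feasibility and acceptability beside them. Section 5.1 describes the benefit of the study in those terms, and Section 6 gives them a qualitative plan with focus groups, interviews and an exit questionnaire. A reader might infer that the study exists to feed a power calculation and otherwise fails; the documents do not support that.

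*Much can be derived anyway.* Marker status is determined for every child tested, and the tables behind a chi-squared or Fisher test contain marker prevalence and attack proportions. Section 7.3 records the timing of withdrawals. The list in Section 11 is described as current, and Sections 4.1 and 6 mention other analyses (summed wheal size, reproducibility). So it would be wrong to say the study can yield none of these figures. What stands is that none is pre-specified. An exact attack rate and its dispersion are also not recoverable from banded answers.

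*The effect may be large.* Section 4.3 reports that children without positive skin tests or raised eosinophils rarely had attacks in the cited crossover trial. A reader might infer from the low power at RR 1.5 that a useful marker would usually appear non-predictive. That holds only for moderate effects; the same assumptions give up to 95% power at RR 2.

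*No decision rule is stated.* Nothing says a marker will be adopted or discarded on p<0.05, and nothing fixes a count outcome for the later trial. The risk is one of interpretation, and dispersion matters only if a count outcome is chosen. The any-attack results above do not depend on that choice.

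**Conclusion.** The concern holds in a limited form. One stated purpose is to supply inputs for a power calculation, and the only statistical plan commits to none of them. Under the assumed ranges, power for a rate ratio of 1.5 is about 16% to 55%, against 39% to 95% for a ratio of 2, and 80% power needs a ratio of 1.72 to 3.19. A p<0.05 reading can therefore miss a marker of moderate effect. All rates, prevalences and dispersions here are assumptions, so the ranges show sensitivity and do not predict what the study will find. The mismatch between purpose and planned analysis does not depend on them. It should be put right, but it does not undermine the feasibility and acceptability aims.

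**What to change.** In Section 11, make estimation the primary analysis, each item with a 95% confidence interval:

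1. Prevalence of each marker.
2. Proportion of children with any attack, overall and by marker status.
3. Retention at 12 months.
4. Attacks per child-year, with the negative binomial dispersion.
5. Rate ratios by marker, or risk ratios for any attack.

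State that p-values are descriptive.

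In Appendix 4, add to Question 3 a numeric field for the number of unscheduled visits in the month. Items 4 and 5 cannot be computed exactly from the bands. Where no count is available, use the any-attack proportion and risk ratio.

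A consent proportion is left off the list because it needs a record of all families approached, including those who decline, and the documents do not describe one.

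The cost is Section 11 wording and one questionnaire field. The drawback is that the report will have no significance result to lead with.

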5. STUDY'S AIM AND OBJECTIVES

AIM: To obtain pilot data to test the hypothesis that aeroallergen sensitisation (confirmed by a wheal formation with a diameter ≥ 3 mm after a skin prick test is performed), FeNO (offline method) ≥ 10 ppb and a peripheral blood eosinophil count $\geq 300/\mu\text{l}$, alone or in combination, can predict future wheezing exacerbations in preschool children as well as response to treatment with inhaled corticosteroids, as a preliminary to a large, randomised controlled trial. Also, that these tests are acceptable to families.

OBJECTIVES:

- To recruit 100 preschool children with a history of wheeze, aged one to five years old, and determine atopic status, peripheral blood eosinophil count (point of care test) and FeNO (offline method).
- To evaluate the feasibility and acceptability of these tests
- To categorize the children according to the biomarkers tested and assess whether any or all, alone or in combination, predict future wheezing exacerbations as well as determine the clinical outcome over one year
- To obtain parents' and doctors' insights into whether the biomarkers mentioned above could be used in a future intervention study.

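### The objective is prediction, but Section 11 plans only tests of group difference at p<0.05, which cannot show how well a biomarker cut-off predicts attacks

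*Combined protocol and SAP*

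**What the plan says.** The aim (protocol Sections 2 and 5) is to obtain pilot data on the hypothesis that a positive skin prick test, FeNO of at least 10 ppb and blood eosinophils of at least 300/µl, "alone or in combination, can predict future wheezing exacerbations in preschool children". A matching objective is to group the children by biomarker and assess prediction over one year. The recruitment objective is "To recruit 100 preschool children with a history of wheeze, aged one to five years old". No power, precision or accuracy target is attached to it.

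Section 4.3 describes an earlier crossover trial and reports that "Those with no positive SPTs or elevated eosinophil count rarely had acute attacks of wheeze". It gives no rate. Sections 4.1 and 6 also speak of predictive power and of the most useful predictor, without naming a measure.

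Section 11 introduces its list with "The tests that are currently planned to be used are". For categorical data it names chi-squared, described as "This test allows assessing if a variable is similar between two or more groups", with Fisher's exact test for small numbers. For quantitative data it names the t-test or Mann-Whitney: "These tests are used for comparison between two study groups". The only criterion is "Level of significance is set as a p value <0.05". No accuracy measure, regression model or confidence interval appears.

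**The concern.** Whether a cut-off predicts attacks depends on four quantities: the share of children with attacks that it flags, the share without attacks that it leaves unflagged, and the attack risk in each marker group. A test of association reports none of these. It shows only that the two risks are unlikely to be equal. A marker with modest accuracy can pass it comfortably at this sample size.

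What is at stake is how the results can be read. If p<0.05 is the only summary planned in advance, a weak marker and a useful one can both be described as significant. The designers of the later randomised trial would also lack planned estimates of attack risk by marker status, which are what a power calculation needs. If accuracy measures are chosen after the data are seen, the choice is open to selection.

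**Working it through.** The plan has no sample-size or accuracy figure to reproduce, so the check asks what accuracy is compatible with p<0.05 at the stated sample size.

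**Inputs from the protocol:** N=100 (Section 5); significance level 0.05, taken as two-sided (Section 11).

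**Assumptions:** attack taken as yes/no over 12 months; share of marker-positive children 15–50%; overall attack rate 30–70%. The protocol gives no figure for either rate. Section 4.1 says only that few preschool wheezers show sensitisation or Type 2 inflammation.

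**Formulas:** let a and b be marker-positive children with and without an attack, and c and d the same for marker-negative children.
- Chi-squared = N(ad−bc)² / [(a+b)(c+d)(a+c)(b+d)]
- Sensitivity = a/(a+c); specificity = d/(b+d)
- PPV = a/(a+b); NPV = d/(c+d)
- AUC of a binary marker = (sensitivity + specificity)/2

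**1. Worked example: 20/30 v 28/70.**
- a=20, b=10, c=28, d=42.
- Chi-squared = 100 × (840−280)² / (30×70×48×52) = 5.98, so p=0.014 (Yates 0.026, Fisher 0.017).
- Sensitivity = 20/48 = 42% (exact 95% CI 28–57). Specificity = 42/52 = 81%.
- PPV = 20/30 = 67%. NPV = 42/70 = 60% (48–72).
- AUC = (0.417+0.808)/2 = 0.61. Of the 48 children with attacks, 28 are marker-negative.

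A second table, 12/20 v 22/80, gives p=0.006 (Fisher 0.009) with sensitivity 12/34 = 35% and NPV 58/80 = 72.5%.

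**2. How general is this?** For each marker frequency, this is the smallest sensitivity that is significant on uncorrected chi-squared, Yates and Fisher together, over attack rates of 30–70%:

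| Marker-positive of 100 | Smallest significant sensitivity |
|---|---|
| 15 | 21–30% |
| 20 | 27–37% |
| 25 | 31–40% |
| 30 | 37–47% |
| 40 | 47–57% |
| 50 | 57–67% |

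Up to 30 marker-positive children, a marker that misses more than half of those with attacks can be significant at every attack rate tried. At 40 it depends on the attack rate. At 50 it cannot be significant.

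**3. How likely is significance?** With true risks of 70% v 40%, simulated tables (chi-squared) reach p<0.05 in 69%, 81% and 86% of cases for 20, 30 and 40 marker-positive children. The true sensitivities are 14/(14+32) = 30%, 21/(21+28) = 43% and 28/(28+24) = 54%. NPV is 60% throughout.

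**4. Does the p-value rank accuracy?**
- 20/30 v 30/70: chi-squared = 100 × (800−300)² / (30×70×50×50) = 4.76, p=0.029, sensitivity 20/50 = 40%, NPV 40/70 = 57%.
- 40/50 v 30/50: chi-squared = 100 × (800−300)² / (50×50×70×30) = 4.76, p=0.029, sensitivity 40/70 = 57%, NPV 20/50 = 40%.

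The p-value is the same, while sensitivity and NPV move in opposite directions.

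**5. A favourable case.** With 12/30 v 7/70, sensitivity is 12/19 = 63% and NPV is 63/70 = 90%. This is also significant: chi-squared = 100 × (756−126)² / (30×70×19×81) = 12.3, p<0.001.

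**The case against.** Several points on the other side stand.

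- **No rule is stated.** A reader might infer that p<0.05 will be reported as prediction, and that such a marker will be carried into the randomised trial. No sentence says either. The test list is described as currently planned, and there is no go/no-go or marker-selection rule. Significance is the only criterion written down, but that is weaker than a rule.
- **This is a pilot.** Section 4.3 assigns confirmation of the earlier trial's findings to a later large randomised trial, with pilot data first. Leaving the low attack risk in test-negative children unconfirmed here is not a failure of the plan. Estimating it is still useful.
- **The examples rest on assumptions.** With more marker-positive children or a lower marker-negative risk, accuracy improves, as steps 2 and 5 show. Section 4.3 points to low risk in children negative on both tests, which favours the better case. The wording in Section 4.1 favours low marker frequency, which is the worse one.
- **Sensitivity for attacks is not the only yardstick.** In Section 4.2 the rationale is "we aim to select out the subgroup of responders who will benefit, while avoiding exposing non-responders to potential side-effects", which concerns response to inhaled corticosteroids. Attacks in children without Type 2 inflammation are expected, so low sensitivity does not make a marker useless for that purpose. The stated objective nevertheless also covers attacks.
- **The counts will exist.** A 2×2 table already contains what PPV and NPV need. That makes the remedy cheap, but the plan does not commit to reporting them or their uncertainty.

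**Conclusion.** The point holds as a mismatch between question and analysis. The objective is prediction, and the planned tests address only group difference. At n=100, with about 30% or fewer children marker-positive and attack rates of 30–70%, p<0.05 is compatible with missing more than half of the children who have attacks. In the worked example sensitivity is 42% and NPV 60% at p=0.014.

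That size depends on marker frequency and attack risks, which the protocol does not give. It would be wrong to read it as saying that a significant marker must be a poor one: at 40% marker-positive with risks of 70% v 40%, sensitivity is 54%, and 12/30 v 7/70 gives 63% with NPV 90%. What does not depend on these assumptions is that the p-value alone cannot tell the cases apart. The documents do not support the further inference that the study will declare a predictor, or select a marker for the trial, on significance alone.

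**What to change.** Add to Section 11, before analysis:

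- For each of the three stated cut-offs, and for skin prick test plus eosinophils combined: attack risk by marker status, sensitivity, specificity, PPV and NPV, with exact 95% CIs. The outcome is at least one attack (unscheduled visit) in 12 months.
- The AUC of the measured values, since a single cut-off discards information.
- A sentence that any statement about prediction rests on these estimates and not on p<0.05.
- For children negative on both skin prick test and eosinophils, the absolute attack risk with its upper 95% limit, labelled as a pilot estimate and not a confirmatory test. As an illustration, 5/50 would read 10%, upper limit 22%.
- A note that all these figures apply under usual-care treatment, because Section 6 leaves treatment to the child's own clinician.

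The cost is a few lines of text and no new data, visits or children. The yes/no outcome is a choice that Section 6.1 does not make. It can be derived from Question 3 of the monthly questionnaire (Appendix 4), which records frequency categories. The intervals will be wide (NPV about ±12 points in the example), and the headline may be less favourable than a significant p-value.

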Allergic sensitisation as determined by skin prick tests, is another association of airway Type 2 inflammation in children, which has been used to predict response to ICS (13). Any biomarker which is of practical use in the management of preschool wheeze has to be able to provide an answer quickly and be available in primary care where most of these children are treated. A portable point of care measurement of peripheral blood eosinophil count from a finger prick blood sample will be carried out in a network of primary health care centres in and around Oxford (a finger prick being the sort of test done repeatedly at home for diabetic children to monitor insulin requirements) and exhaled nitric oxide measurements, meaning that both tests are practical by the above criteria.

Finally, it should be noted that atopy is not an 'all-or-nothing' phenomenon (14). We propose to perform exploratory, hypothesis generating analyses quantifying atopy by the sum of skin prick test wheals, to see if the predictive power of this test can be further improved.

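### The objective covers prediction by the three markers in combination, but no analysis in Section 11 estimates what a second or third marker adds

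*Combined protocol and SAP*

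**What the plan says.** Sections 2 and 5 make prediction by the markers, singly and jointly, part of the aim. The objective in Section 5 is "To categorize the children according to the biomarkers tested" and then to "assess whether any or all, alone or in combination, predict future wheezing exacerbations as well as determine the clinical outcome over one year". The recruitment target is 100 children.

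Section 11 introduces its list with "The tests that are currently planned to be used are" and sets "Level of significance is set as a p value <0.05". It names a normality check and four procedures. Chi-squared is described this way: "This test allows assessing if a variable is similar between two or more groups or to test if two or more variables are related/dependent". For small samples the section turns to Fisher's exact test. Of the t-test and Mann-Whitney it says "These tests are used for comparison between two study groups". The documents mention no regression, stratified or adjusted contrast, interaction, discrimination measure or confidence interval.

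Outside Section 11, the predictive analyses mentioned are an exploratory sum of wheals (Section 4.1) and a look at which aeroallergen predicts best (Section 6). Both refine the skin test; neither combines it with another marker.

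Section 4.1 introduces FeNO as a further marker of eosinophilic airway inflammation and says that skin-test sensitisation "is another association of airway Type 2 inflammation in children". Section 6 reads raised FeNO and raised blood eosinophils alike as Type 2 inflammation.

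**The concern.** Whether a marker predicts attacks and whether it adds to another marker are different questions. The objective asks both, and the listed tests are suited only to the first. If the markers overlap, each unadjusted comparison carries part of the others' association, and putting the three results side by side does not show which markers are needed together.

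This matters for the next study. Section 4.3 wants pilot data to inform power calculations. It also reports that, in earlier work on response to regular inhaled steroids, skin test plus eosinophils did better than eosinophils alone. Section 5.1 looks ahead to a trial using one or more of the markers. Planners would want to know whether a second or third test earns its place, and the listed analysis would give them no estimate of that.

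**Working it through.** **The plan's own figure.** The target of 100 comes with no effect size, attack rate, marker prevalence, power or precision, so it cannot be reproduced. Except for the 100, every input below is an assumption.

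**1. Crude ratio for a marker that adds nothing.** Assume eosinophils are positive in 30% of children, and the skin test is positive in 60% of eosinophil-positive and 20% of eosinophil-negative children, with no effect of its own.
- P(skin+) = 0.3×0.6 + 0.7×0.2 = 0.32
- P(eos+ | skin+) = 0.18/0.32 = 0.5625; P(eos+ | skin−) = 0.12/0.68 = 0.176
- Crude rate ratio for true eosinophil ratio R = [1 + (R−1)×0.5625] / [1 + (R−1)×0.176]
- R = 1.5 gives 1.18; R = 2 gives 1.33; R = 2.5 gives 1.46
- With no overlap beyond chance, the ratio is 1.0 for any R
- Implied correlation: phi = (0.18 − 0.3×0.32)/√(0.3×0.7×0.32×0.68) = 0.084/0.214 = 0.39

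**2. How often such a marker reaches p<0.05.** This was simulated with 3,000 studies of 100 children per scenario, both markers at 30% or both at 40% prevalence, and risk of any attack 30% v 60% or 40% v 70% by the first marker. The second marker has no effect of its own.

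| phi | unadjusted, as listed | adjusted for the first marker |
|---|---|---|
| 0 | about 5% | 4–5% |
| 0.3 | 13–15% | 4–5% |
| 0.5 | 30–32% | 4–5% |
| 0.7 | 50–55% | 4–5% |

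**3. Profile sizes.** Give FeNO the same 60%/20% relation to eosinophils, independent of the skin test once eosinophils are known.
- All three positive: 100×0.3×0.6×0.6 = 10.8
- Eosinophils only: 100×0.3×0.4×0.4 = 4.8
- None positive: 100×0.7×0.8×0.8 = 44.8
- For comparison, full independence at 30% each gives 100×0.3³ = 2.7 triple-positive children

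**4. Precision of the alternatives.** For illustration, take a mean of 1.5 attacks a year and dispersion 1, so SE(log ratio) ≈ √[(1/n₁ + 1/n₀)×(1/1.5 + 1)]. The 95% interval is the estimate multiplied and divided by exp(1.96×SE).
- Skin test, crude, 32 v 68: SE 0.277, factor 1.7
- Skin test within eosinophil-positive children only, 18 v 12: SE 0.481, factor 2.6
- Skin test adjusted for eosinophils, all 100: SE ≈ 0.277/√(1−0.39²) = 0.301, factor 1.8
- Eosinophils, crude, 30 v 70: SE 0.282, factor 1.7
- Eosinophils adjusted for both others: correlation of skin test with FeNO = 0.39² = 0.154; R² = 2×0.154/(1+0.154) = 0.27; SE ≈ 0.282/√(1−0.27) = 0.329, factor 1.9

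Mutual adjustment therefore raises the standard error by about 9% to 17% under these assumptions. It is tighter than the within-stratum contrast because it uses every child.

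**5. What the form can supply.** Appendix 4, Question 3 records emergency appointments in frequency bands; the lowest non-zero band merges one with two. It shows whether a month had any visit, but not an exact count.

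**The case against.** The strongest reply is that the objective is about prediction, and a marker that tracks another does predict. That stands. The crude ratio of 1.33 is a valid answer to the question about a marker alone, and unadjusted tests suit that question. A reader might infer from the simulation that 13–55% of studies would report a false predictor. The documents do not support that: those results are true associations, and they mislead only if read as added value.

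A reader might also infer that combinations cannot be examined at all. That goes too far. Children will be categorised by biomarker, chi-squared allows more than two groups, and a two-group test could compare skin-positive with skin-negative children among the eosinophil-positive. But the plan names no such contrast, and a p-value across profiles does not estimate an increment. Nor does the plan propose testing a combination against all other children.

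A third tempting reading is that the triple-positive group would be hopelessly small. The figure of 2.7 requires independent markers; with the overlap assumed above it is 10.8.

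Overlap itself can be questioned. Section 6 reads a positive wheal as sensitisation, and Section 4.1 says many atopic wheezers lack an eosinophilic airway phenotype. That points to partial overlap, the situation in which adjustment is informative.

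Finally, this is a feasibility study with a provisional test list and statistical support, and nothing says its p-values will choose the future trial's markers. That lowers the weight of the point without closing the gap between objective and analysis.

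**Conclusion.** The point holds for the in-combination half of the objective: followed as written, Section 11 yields no estimate of what one marker adds to another. The half about each marker alone is adequately served by unadjusted tests.

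That gap is certain from the text; its size is not. The crude ratio of about 1.2 to 1.5 for a redundant skin test rests on assumed prevalence (30%), overlap (60% v 20%) and a true eosinophil ratio of 1.5 to 2.5. It falls to 1.0 if the markers are independent. The change should be made before analysis, but the omission does not undermine the feasibility and acceptability aims.

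**What to change.** In Section 11:

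- Keep the single-marker comparisons, labelled as answering the question about each marker alone.
- Add one exploratory model with the three markers entered together, reporting mutually adjusted estimates with 95% confidence intervals.
- Use an outcome that Appendix 4 supports: months with at least one unscheduled visit, with months of completed follow-up as denominator or offset; or any attack, by logistic regression. Use a negative binomial attack count only if Question 3 is changed to record a number.
- Report the attack rate by number of positive markers (0 to 3) and the eight-profile table as description only. The 0-to-3 count weights the markers equally, so it cannot show which one matters.

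The cost is SAP wording and one model by the collaborating statistician. The downsides are somewhat wider intervals than the unadjusted ones, an assumption of no interaction between markers, and possibly software other than the package named in Section 11, whose suitability was not checked here.
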